15.5.2.4 Conversion to Secondary Interventions

In important endpoint for subjects enrolled in this study will be conversion to alternative treatments. The protocol allows for a single intra-articular corticosteroid injection into the knee to manage knee pain without necessitating removal of the subject from the study. However, if a study subjects elects to convert to a regenerative medicine treatment (e.g. platelet rich plasma or bone marrow aspirate concentrate) or a surgical intervention (e.g. microfracture or total joint replacement), they will be removed from the study. Cox proportional hazards regression will be performed to compare the hazard rate of conversion to each of these two treatment categories between treatment groups.

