9.1 Enrollment Criteria

9.1.1 Inclusion Criteria

Subjects will be included if all of the following criteria are met:

1. Are male or female, ages 40-80;
2. Are willing to comply with all study related procedures and assessments;
3. Are ambulatory as defined by ability to complete functional performance testing;
4. Radiographic evidence of Kellgren-Lawrence grade II-IV osteoarthritis in one or both knees;
5. Scores 4-10 on the Numerical Rating Scale (NRS) for pain;
6. Stable dose of screening/baseline medications for at least 2 months prior to the anticipated date of study drug dosing.

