15.2 Study Design

The study will follow a two-arm, double-blind, placebo-controlled approach. Allocation will be 1:1 between the two groups. Study subjects, treating physicians, medical assistants, and other members in the research team who conduct subject contact and/or data analysis will remain blinded throughout the study period.

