15.3 Randomization

To better ensure equivalent group sizes in the event of unenrollment or loss-to-follow-up, a block randomization scheme will be followed with block size of $n=8$. The following steps will be adhered to when enrolling a subject into one of the two study arms:

1. Eight tokens, numbered 1-8, will be held in a jar stored in the study manager's office within TSC and SPRI.
2. Upon enrollment, a token will be drawn from the jar, and not replaced back into the jar.
3. The Block Number and Within-Block Number will be recorded by the study team on a blinded version of the Enrollment/Randomization log.
4. The Block Number and Within-Block Number will be disclosed to the Vail Health Hospital Pharmacy who will arrange the proper medication and record the subject onto an unblinded version of the Enrollment/Randomization log.

-
- When final token is taken from jar, enrollment within that block is complete, and all 8 tokens will be placed back in the jar in preparation for the next subject and the new block.

Figure 15.3 Portion of the randomization/enrollment log demonstrating group allocation for subjects enrolled into block #1.

Block Number	Within-Block Number	Group (Randomization not finalized, for illustration only)	Subject ID
		Patient	
		Enrollment	
		Date	
1	1	Fisetin	1
	2	Placebo	2
	3	Placebo	3
	4	Fisetin	4
	5	Placebo	5
	6	Fisetin	6
	7	Fisetin	7
	8	Placebo	8

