15.4 General Data Handling, Analysis, and Reporting Strategy

Intent-to-treat analysis will be performed.

Baseline covariates will be summarized and reported in a table, stratified by group. This is a randomized trial, thus the expected population group differences with respect to baseline covariates are zero by definition. For this reason, no statistical comparisons will be performed to test for differences in baseline covariates between groups.

Whenever applicable, assessment of endpoints that are measured at serial time points will be analyzed using methods that account for this repeated measure structure. Listwise deletion in response to missing data points and categorization/dichotomization of continuous measurements will be avoided to every extent possible.

Summary statistics will be reported as group medians with quartiles or extrema. Meanwhile estimates calculated for statistical inference will be reported with $(1-\alpha)\%$ confidence intervals. Model fit and satisfactorily meeting model assumptions will be assessed for all multivariable regression and linear mixed-effects models using residual analysis.

The Statistical Computing Language R will be used to produce all analyses and plots.

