15.5.2 Secondary Endpoints

15.5.2.1 Imaging Assessment of OA

Quantitative MRI will be performed at baseline and at 6 months and 12 months after initiation of medication. T2 and T1rho relaxometry will be performed. Linear mixed-effects modeling with random intercepts will be used to appropriately match the repeated measures design. A group-by-time interaction will be modeled to investigate both early improvement in tissue quality and maintenance of such an effect to 12 months as well.

Secondarily, multivariable modeling techniques such as support vector machines (SVM) and/or principal components analysis (PCA) will be pursued to characterize the SASP response profile that distinguishes the FIS and placebo groups.

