15.5.2.2 Kinematic, Strength and Functional Performance Testing

Measurements from the timed-up-and-go test (TUG), 4-meter walk test (4mW), 6-minute walk test (6MW), time to descend 9-12 stairs test (SCT), video motion capture of lower-extremity kinematics, and isokinetic muscle test using the HUMAC NORM system will be assessed as continuous variables. Previous testing has identified these measurements follow a relatively Gaussian distribution, so parametric comparison of means (Welch's t-test) is planned between treatment groups.

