15.5.2.3 Pain and PRO Assessment

The hypothesis in this study is that FIS will induce a systemic anti-inflammatory and senolytic effect, thereby reducing pain and improving self-reported function and quality of life compared to the placebo group. Early subjective assessment (every 3 days for 6 weeks following the first dose of study medication and once weekly for the following 6 weeks) will be limited to a short augmented numerical rating scale questionnaire. Linear mixed-effect random-intercepts modeling will be used to characterize the trend in self-reported pain over 3 months, and to test whether treatment group is a significant predictor of pain reduction.

The IKDC, WOMAC, Tegner activity scale and Lysholm PRO measures will be administered at 2 weeks after the last dose of study medication and 6, 12, and 18 months following initiation of medication. For each time point, ANCOVA will be used with the subject's baseline PROM value used as a covariate. Among the 4 postoperative time-points for assessing these validated PROMs, the Holm-Bonferroni method will be used to control the family-wise type-1 error rate to 0.05 within each PROM scale tested. No multiplicity adjustments will be made across different PROMs, which are commonly highly intercorrelated.

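### The Cox analysis of conversion to alternative treatment ignores Kellgren-Lawrence grade, so its hazard ratio is open to chance imbalance in baseline severity

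*Combined protocol and SAP*

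**What the plan says.** - **Eligibility (Section 9.1.1):** "Radiographic evidence of Kellgren-Lawrence grade II-IV osteoarthritis in one or both knees". Section 10.0 (Visit 1) and Appendix B use a radiograph to confirm this. Section 11.6.1 accepts a satisfactory film from the 6 months before screening.
- **Allocation (Sections 15.2 and 15.3):** "Allocation will be 1:1 between the two groups", and "a block randomization scheme will be followed with block size of" eight. No stratification factor is named.
- **Baseline covariates (Section 15.4):** "Baseline covariates will be summarized and reported in a table, stratified by group". The section declines to test baseline differences because their expected value is zero under randomization. It gives no covariate a role in any model.
- **Conversion (Section 15.5.2.4):** "Cox proportional hazards regression will be performed to compare the hazard rate of conversion to each of these two treatment categories between treatment groups". Treatment group is the only term. The section calls conversion an important endpoint and counts total joint replacement among the surgical events.
- **Labels (Section 15.8):** group codes A and B are added to the data as the last step before analysis.

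**The concern.** Radiographic severity is a plausible driver of the decision to have surgery or another intervention, and the trial spans three grades of it. For most other efficacy outcomes the subject's own starting value carries part of that severity. Time to conversion has no starting value, so nothing in the planned model stands in for it.

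Section 15.4 is right that the expected imbalance is zero, but that does not make the realized imbalance zero. If one arm happens to receive more grade IV knees, the reported hazard ratio reflects that as well as the treatment. If the baseline table then shows a gap and adjustment is added, the adjustment is post hoc and open to challenge.

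**Working it through.** **1. Arm size.** The plan's only sample-size figure is for a comparison of means (Section 15.6: SMD 0.73, two-sided 0.05, 80% power).

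n per group = 2(1.960 + 0.842)² / 0.73² = 29.5, so 30. This reproduces the plan's figure. Adding 20% gives 30 × 1.2 = 36 per arm, as in Section 6.0. The stated ceiling of 100 subjects gives 50 per arm, so both sizes are used below. The plan gives no event count or power for conversion.

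**2. Chance of imbalance in grade IV.** The number of grade IV knees in each arm is taken as binomial (n, p), independent between arms, which is unstratified allocation. The share p is assumed to be 20-40%. All pairs of counts are enumerated exactly, in either direction:

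| Per arm | Gap | p = 20% | p = 30% | p = 40% |
|---|---|---|---|---|
| 36 | 10 points or more | 30% | 37% | 40% |
| 36 | 20 points or more | 3% | 5% | 7% |
| 50 | 10 points or more | 26% | 33% | 36% |
| 50 | 20 points or more | 2% | 4% | 5% |

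By symmetry, half of each figure is imbalance against the active arm. At 36 per arm, 10 points means at least 4 patients (4/36 = 11%).

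**3. Rough size of the shift.** Assume that grade IV doubles the conversion hazard.
- Shares of 30% versus 40% multiply the hazard ratio by about (1 + 0.4)/(1 + 0.3) = 1.08, a log shift of 0.074.
- Shares of 30% versus 50% give 1.5/1.3 = 1.15, a log shift of 0.143.
- The standard error of the log hazard ratio is about 2/√events: 0.52 at 15 events and 0.37 at 30.
- The shifts are therefore 0.14-0.20 and 0.28-0.39 standard errors.

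**4. Simulated Cox models.** Assumed: equal thirds of grades II, III and IV; 20-40% control conversion by 18 months; 36 or 50 per arm; true hazard ratio 0.5 (or 1.0 for type I error).
- *Grade as one ordinal term, hazard ratio 1.5-2.0 per grade.* The overall median is 0.48-0.53 without grade and 0.48-0.50 with it. Power goes from 12-46% to 13-49%. When the active arm is worse by at least 0.25 grade on average, the median is 0.54-0.66 without grade and 0.46-0.55 with it.
- *Stratified by IV versus II-III.* When the active arm has at least 10 points more grade IV knees, stratification mostly removes the shift. At the strong end of the assumptions (3 per grade) the median is 0.70 unadjusted and 0.50 stratified. At 1.5-2.0 per grade, power changes by only -1 to +3 points. The standard error is at most about 1-2% larger.
- Type I error is 3-6% with or without grade.

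**5. Events needed.** For 80% power at a hazard ratio of 0.5, events = 4(1.960 + 0.842)² / (ln 0.5)² = 65.3, so 66. With 15-30 events, power is 27-48%. The analysis is imprecise with or without grade.

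**The case against.** The strongest reply is that nothing is invalid. Chance imbalance is already covered by the type I error and the confidence interval, and the simulations agree. Sampling noise also exceeds the likely shift: at a doubled hazard, even a 20-point gap moves the estimate by less than 0.4 standard errors. The grade mix and its prognostic strength are outside assumptions, and Section 15.6 itself reports little literature comparing grades of advanced disease. Events will probably be few and are divided over two conversion categories. The primary endpoint is safety. All of this stands, and it is why the point has low priority. It does not remove the case for fixing, in advance, a cheap adjustment that protects the estimate in an unlucky sample.

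A reader might infer that grade belongs in every efficacy model. The documents do not support that.
- **MRI (Section 15.5.2.1):** "A group-by-time interaction will be modeled to investigate both early improvement in tissue quality and maintenance of such an effect", in a mixed model that includes the baseline scan. More grade IV knees in one arm shift its level, not its change. A main effect of grade leaves the group-by-time contrast unchanged with complete data and almost unchanged with missing scans.
- **Questionnaires (Section 15.5.2.3):** the ANCOVA already uses the subject's own baseline score.
- **Function and strength (Section 15.5.2.2):** "parametric comparison of means (Welch's t-test) is planned between treatment groups". That test takes no covariate. The plainer gap there is that no use of the Visit 2 baseline is stated, and grade would be a poor substitute.

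It is also only inferred that a three-level grade is on file. The documents ask the radiograph to confirm eligibility and refer to one or both knees.

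**Conclusion.** The point holds for the conversion analysis alone. The planned Cox model leaves its hazard ratio exposed to chance imbalance in KL grade, and no baseline value of the outcome offsets this. At 36 per arm, a gap of 10 points or more against the active arm would arise in about 15-20% of trials (half of 30-40%). The resulting shift is small at a doubled hazard and clear only if grade is strongly prognostic.

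This rests on three assumptions that the documents do not supply: the grade IV share, the effect of grade on conversion, and the conversion rate. Two stronger conclusions might be drawn and should not be. The plan is not biased, because the unadjusted comparison is valid under randomization. Nor does adjustment buy precision: the standard error is no smaller, and average power barely moves at the moderate grade effects assumed. The benefit is a hazard ratio that is easier to interpret when the arms happen to differ.

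**What to change.** 1. State in Section 10.0 or 11.6.1 that the KL grade (II, III or IV) of the Study Knee is recorded from the screening radiograph, or from the accepted earlier film.
2. In Section 15.5.2.4, before the group codes of Section 15.8 are attached, prespecify the Cox model stratified by grade IV versus II-III, or with grade as a single ordinal term. Choose one of the two in advance.
3. Report the unadjusted hazard ratio beside it in all cases.

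Randomization and the other efficacy models need no change on this account. The cost is a few lines of text, one data field, and one extra stratum or term where events are scarce. Where conversions in a category are very few, the stratified estimate may be unstable, which is a further reason to show both results.

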15.6 Statistical Power and Sample Size

Anticipated effect sizes for the group difference with respect to MRI-assessed cartilage quality were derived from the literature, however a paucity of literature was found in the knee OA literature when comparing various grades of advanced osteoarthritis. As a simplifying assumption, we derived an anticipated effect size for clinically meaningful change in T1rho values from a recent meta-analysis (MacKay, et al, 2018, J Osteoarthritis and Cartilage) that reported the standardized mean difference (SMD) between mild OA and healthy controls.

We aim to power this study to detect an effect size between the FIS and placebo treatment groups that is equal to the meta-analyzed effect size described above (SDM=0.73). The statistical method for this unadjusted, independent groups comparison of means, and the significance level will be set at $\alpha=0.05$. Assuming 2-tailed testing and requiring 80% statistical power, 30 patients per group are sufficient to detect the effect size of interest. Anticipating a 20% drop-out or incomplete follow-up rate, we aim to enroll no more than 100 total OA patients (30 per groups, and 6 per group to account for 20% drop out). Power calculations were performed using G*Power (version 3.1; Universität Düsseldorf).

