3.0 Study Synopsis

Sponsor/ Investigator Sponsored Study	[name].
Study Title:	Senolytic Drugs Attenuate Osteoarthritis-Related Articular Cartilage Degeneration: A Clinical Trial
Protocol Number:	2019-16
Study Design:	Randomized, double-blind, placebo controlled
Study Duration:	Approximately 36 months Enrollment 18 months Follow-up 18 months
Randomization:	Subjects are to be assigned to one of two treatment groups using a 1:1 (Fisetin/placebo) randomization scheme.
Study Arms/Medication	Active Treatment: Fisetin 100 mg capsules (~20 mg/ kg/ day) will be administered orally for two consecutive days (days 1 and 2) followed by 28 days off. A second course will be given for two consecutive days (days 31 and 32) Placebo Control: Appearance matched capsule p.o. dose to match the number of capsules as if subjects were receiving active treatment. Placebo capsules will be administered orally for two consecutive days (days 1 and 2) followed by 28 days off. A second course will be given for two consecutive days (days 31 and 32)
Blinding Procedure:	The block randomization chart will be securely kept by an Unblinded Study Team member and at the Vail Hospital Pharmacy (point of subject distribution). All study subjects and other Study Team members including the Principal Investigator will be blinded to treatment through 18 months follow-up. In addition, any individuals engaged by the Principal Investigator to provide and/or document assessment of study endpoints will be blinded to treatment.
Sample Size and Study Population:	A total of 100 male or female subjects 40-80 years of age will be recruited from a single clinical site, where the Principal Investigator conducts patient care.
Objectives:	Primary Objective

	
To evaluate as compared to placebo:
 
The safety of administering Fisetin in subjects with osteoarthritis (OA) of the knee.
 
Secondary Objectives
 
To evaluate as compared to placebo:
 
 1. Reduction of pro-inflammatory and cartilage degenerating SASP markers; 2. Improvement in physical function of the Study Knee; 3. Improvement in patient reported outcomes; 4. Improvement in the quality of articular cartilage in the Study Knee with quantitative magnetic resonance imaging (MRI); 5. Reduction in time to conversion to alternative treatment.

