6.0 Summary of Proposed Placebo Controlled Trial

Our objective is to determine (through the performance of an adequate and well-controlled clinical trial) if the administration of Fisetin (FIS) safely reduces inflammation and pain, reduces senescent cell burden, mitigates cartilage degeneration, and improves joint function in patients with moderate to severe OA of the knee.

Patients suffering from OA of one or both knees will be recruited from the clinical practice of the Principal Investigator at TSC. Patients diagnosed with Kellgren-Lawrence grade II-IV OA of the knee via radiographic analysis, who meet all enrollment criteria will be offered the opportunity to participate in this study.

At the first visit, each potential subject will be fully informed regarding all aspects of the proposed study and will be required to review and sign a full, IRB approved, Informed Consent Form (ICF) attached as **Appendix A in Section 22.1**. Subjects who sign Informed Consent will be screened by a member of the Study Team. The patients' medical record will be reviewed to determine if medical history indicates that the eligibility criteria are met. If so, subjects will be screened for OA and senescent cells by T-Cell assay, C12FDG Flow assay, and by senescence biomarker assay. Further blood analyses will be performed.

Subjects who meet eligibility criteria will be assigned, 1:1 via block randomization, to one of the two blinded study groups. FIS and the inactive placebo are collectively referred to as Study Medication.

n=36: Active Treatment: FIS: 100 mg capsules (~20 mg/ kg/ day);

n=36: Placebo Control: Appearance matched capsules (dose to match the number of capsules as if subjects were receiving active treatment).

At visit two, Quantitative MRI, kinematic movement and strength testing, range of motion (ROM) and functional performance testing. Subjects will complete numerous patient reported outcomes tools, including an augmented patient reported outcomes (PROs), including numerical rating scale (NRS) for pain (as described in **Section 11.5**) of this protocol International Knee Documentation Committee (IKDC), Lysholm, Tegner, Western Ontario McMaster Universities Osteoarthritis Index (WOMAC) and short form-12 health survey (SF-12), which will provide a baseline assessment of joint pain and function.

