7.5 Study Design and Duration

7.5.1 Study Design

This is a prospective, randomized, placebo controlled, double blind study to be conducted at the Steadman Clinic and the Steadman Philippon Research. A total of no more than 100 will be randomized 1:1 to receive either Fisetin (FIS) or placebo.

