8.2 Study Endpoints

8.2.1 Primary Endpoint:

1. Occurrence of adverse events.

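### Sections 15.6 and 6.0 give 72 patients, the synopsis gives 100 without explanation, and the allowance of 6 per arm covers 16.7% loss rather than the stated 20%

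*Combined protocol and SAP*

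**What the plan says.** Section 15.6 sizes the trial on T1rho. The difference to be detected is "equal to the meta-analyzed effect size described above (SDM=0.73", for an unadjusted comparison of two independent means at two-tailed alpha 0.05. It concludes that, "requiring 80% statistical power, 30 patients per group are sufficient to detect the effect size of interest". It then anticipates 20% drop-out or incomplete follow-up and writes "we aim to enroll no more than 100 total OA patients (30 per groups, and 6 per group to account for 20% drop out".

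Three other places give a size:

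- Section 6.0: "n=36: Active Treatment: FIS: 100 mg capsules", with the same number for placebo.
- Section 3.0, Study Synopsis: "A total of 100 male or female subjects 40-80 years of age will be recruited from a single clinical site".
- Section 7.5.1: "A total of no more than 100 will be randomized 1:1".

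The primary endpoint in Section 8.2.1 is "Occurrence of adverse events". Section 15.6 does not size the trial for it.

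**The concern.** In Section 15.6 the derivation stands in brackets directly after the figure of 100, as though it explained that figure, but it produces 72. Section 6.0 carries 72 as the design, while the synopsis carries 100 as the total. A reader cannot tell which is the target, or why enrolment may run 28 patients (28/72 = 39%) above the derived size. Stopping at 72, at 100 or anywhere between would fit some section of the plan.

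The dropout allowance is a separate slip. To keep 30 evaluable per arm after losing 20%, the evaluable number has to be divided by 0.80. The plan multiplies it by 1.20.

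Two things are at stake: whether the power requirement is met at the size actually enrolled, and how precisely adverse events, the primary endpoint, can be described.

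**Working it through.** **Inputs.** From 15.6: standardized difference d = 0.73, two-sided alpha 0.05, power 80%, 30 evaluable per arm, 20% loss, 6 added per arm. Allocation is 1:1 (15.2). Stated sizes are 36 per arm (6.0), 100 in total (3.0) and at most 100 randomized (7.5.1).

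**Reproducing the 30.** By the normal approximation, n per arm = 2(1.960 + 0.842)²/0.73² = 29.5, which rounds up to 30. The plan's figure reproduces. The exact two-sample t-test needs 30.4, so 31; at 30 per arm its power is 79.4%.

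**Reproducing the 36.** 30 × 1.20 = 36 per arm, and 2 × 36 = 72, in agreement with 6.0.

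**Checking the dropout allowance.**

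- Loss that 36 can absorb: 6/36 = 16.7%.
- Left after 20% loss: 36 × 0.80 = 28.8 per arm.
- Needed to keep 30: 30/0.80 = 37.5, so 38 per arm, 76 in total.
- Needed to keep 31: 31/0.80 = 38.75, so 39 per arm, 78 in total.

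**Trying to reach 100.** With 50 per arm, ending at 30 evaluable would need a loss of 1 − 30/50 = 40%, twice the stated rate. No stated input leads to 100.

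**Power for d = 0.73 after 20% loss.** The normal approximation is Φ(0.73·√(n/2) − 1.960); the exact figure uses the noncentral t distribution.

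| Enrolled | Evaluable per arm | Exact t | Normal approximation | Difference detectable with 80% power (exact t) |
|---|---|---|---|---|
| 72 | 28.8 | 77.7% | 79.1% | 0.75 |
| 76 | 30.4 | 79.9% | 81.2% | 0.73 |
| 78 | 31.2 | 81.0% | 82.2% | 0.72 |
| 100 | 40 | 89.7% | 90.4% | 0.63 |

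The slip alone moves evaluable patients from 30 to 28.8 per arm: 79.4% to 77.7% by exact t (1.7 points), or 80.7% to 79.1% by the normal approximation (1.6 points).

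**Adverse events.** Assume that everyone randomized is dosed. For an event type never seen among n Fisetin patients, the one-sided 95% upper bound on its rate is 1 − 0.05^(1/n). That is 8.0% with n = 36 and 5.8% with n = 50.

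**The case against.** The strongest reply is that nothing is contradicted. Sections 15.6 and 7.5.1 give a ceiling, and 72 lies below it. Only the synopsis states 100 flatly, and it speaks of recruitment, which might be read as a count before screening. The ceiling point stands: those two sections are compatible with 72. The screening reading has little support, because the synopsis does not say so and 7.5.1 applies the figure of 100 to patients randomized. The synopsis total still has no derivation.

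Other objections concern weight, and several are fair:

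- The dropout slip is small and has no consequence if 100 are enrolled.
- Part of the shortfall below 80% is not due to dropout. By exact t, 30 per arm without any loss already gives only 79.4%.
- The planned MRI analysis differs from the sizing test: "Linear mixed-effects modeling with random intercepts will be used to appropriately match the repeated measures design". Patients with partial follow-up would contribute to that model, so counting all of the 20% as lost is a sizing convention.
- The safety bounds illustrate what the choice of size changes. The plan makes no sample-size claim for adverse events, so they show no error in it.
- Section 15.3 uses blocks of 8. Seventy-two is 9 complete blocks, but 76, 78 and 100 are 9.5, 9.75 and 12.5, so exactly equal arms are not guaranteed at those sizes.

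None of this supplies the missing step from 72 to 100 or makes 6 of 36 equal to 20%.

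**Conclusion.** The concern holds on both counts. The plan derives 72 and states 100 in its synopsis, with no explanation of the difference. Its dropout allowance covers 16.7% loss, not 20%.

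The unreconciled total matters more: it separates a sizing calculation slightly below its own 80% requirement from one with about 10 points to spare. The dropout slip is minor by itself. Neither makes the trial invalid, but the target size is a core design figure, so this should be corrected.

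The power figures assume d = 0.73, equal arms, a two-sample t-test at two-sided alpha 0.05, and that the 20% lost contribute nothing. They say nothing direct about power for adverse events or under the mixed model.

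**What to change.** State one target number in 3.0, 6.0, 7.5.1 and 15.6, and report its power. A ceiling may stand beside the target if it is labelled as one and explained. The choice is the sponsor's:

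- **Keep 72.** Change the synopsis figure and report about 78% power after 20% loss, or 80% power for a difference of 0.75.
- **Keep 100.** Change the 36 per arm in 6.0, replace the 30-plus-6 derivation, give the reason for the larger number, and report about 90% power after 20% loss, or 80% for a difference of 0.63.
- **Keep the dropout derivation but correct it.** Divide by 0.80. Thirty evaluable gives 38 per arm (76 total), 79.9% by exact t; 31 evaluable gives 39 per arm (78 total), 81.0%. Sections 3.0 and 6.0 then both change.

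In each case, say whether the power comes from the exact t-test or the normal approximation, and that it refers to the two-sample sizing calculation for T1rho and not to the mixed model. If the chosen total is not a multiple of 8, say how the last block is handled.

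The cost is wording in four sections. Every option stays within the ceiling of 100, although 76 or 78 would exceed the 72 now in 6.0. If 72 is kept, the reported power falls from 80% to about 78%.

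### Section 15.6 covers 20% dropout by adding 20% of 30 instead of dividing by 0.80, so 36 per group falls about 2 points short of 80% power if enrolment stops at 72

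*Combined protocol and SAP*

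**What the plan says.** Section 15.6 sizes the trial on T1rho. The target effect is "equal to the meta-analyzed effect size described above (SDM=0.73", the test is an unadjusted comparison of two independent means at a significance level of 0.05, and the conclusion is: "Assuming 2-tailed testing and requiring 80% statistical power, 30 patients per group are sufficient to detect the effect size of interest". The dropout step follows: "Anticipating a 20% drop-out or incomplete follow-up rate", with the parenthesis "30 per groups, and 6 per group to account for 20% drop out". The sentence containing that parenthesis also sets a ceiling of 100 patients in total.

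The sizes given elsewhere are:
- Section 6.0 lists "n=36: Active Treatment: FIS: 100 mg capsules (~20 mg/ kg/ day" and the same number for placebo, so 72 in total.
- The Synopsis (3.0) gives a total of 100 subjects.
- Section 7.5.1 gives 100 as an upper limit, randomised 1:1.

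**The concern.** An allowance for dropout should leave the required number of evaluable patients after the loss. Adding 20% of the required number does not do so, because the loss applies to the larger number enrolled. Going from 36 to 30 is a loss of 6/36 = 16.7%, not 20%.

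Section 15.6 is the only quantitative justification of the trial's size. If 36 per arm is what will be enrolled, the plan does not reach its stated 80% power under its own dropout assumption. The section also derives 72 while permitting 100, so a reader cannot tell which enrolment the 80% describes.

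**Working it through.** **Inputs, all from section 15.6:** SMD d = 0.73 (so SD = 1); two independent groups of equal size; two-sided alpha 0.05; power 80%; dropout 20%; 30 evaluable and 36 enrolled per group. The 36 also appears in section 6.0, and the total of 100 in the Synopsis and section 7.5.1.

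**Step 1: reproduce the base of 30.** Normal approximation:

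n = 2(1.960 + 0.842)² / 0.73² = 2 × 7.849 / 0.5329 = 29.46, rounded up to **30 per group**.

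The plan's figure is reproduced. Normal-approximation power at 30 is Φ(0.73 × √(30/2) − 1.960) = Φ(0.867) = 80.7%. The exact two-sample t-test (noncentral t, 2n − 2 degrees of freedom, noncentrality d√(n/2)) gives 79.4% at 30 and 80.7% at 31, so its minimum is 31.

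**Step 2: the dropout allowance.**
- As written: 30 × 1.20 = 36, and 36 × 0.80 = 28.8 evaluable.
- As needed from a base of 30: 30/0.80 = 37.5, so **38 per group (76)**.
- As needed from the exact-t base of 31: 31/0.80 = 38.75, so **39 per group (78)**.

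**Step 3: power at SMD 0.73, two-sided alpha 0.05.**

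| Evaluable per group | How it arises | Exact t | Normal approximation |
|---|---|---|---|
| 28 | 28.8 rounded down | 76.5% | 78.0% |
| 28.8 | 36 enrolled, 20% lost | 77.7% | 79.1% |
| 29 | 28.8 rounded up | 78.0% | 79.4% |
| 30 | plan's requirement | 79.4% | 80.7% |
| 31 | exact-t minimum | 80.7% | 82.0% |
| 40 | 50 enrolled, 20% lost | 89.7% | 90.4% |

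The number lost will vary by chance. If each patient independently has a 20% chance of loss, average exact-t power is 77.4% with 36 enrolled per group, 79.7% with 38, 80.7% with 39 and 89.5% with 50.

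**Step 4: the same shortfall as an effect size.** At 30 per group the SMD detectable with 80% power by exact t is 0.736. At 28.8 it is about 0.736 × √(30/28.8) = 0.75.

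**The case against.** Four replies deserve weight.

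*The ceiling of 100 makes the shortfall hypothetical.* This stands in part. At 50 per group, power after 20% loss is about 90%. But section 15.6 and section 7.5.1 give 100 as a limit, only the Synopsis states it as the total, and section 6.0 fixes 36 per arm. The only derivation in the plan ends at 36, and nothing supports 100 by calculation. Enrolling 72 would comply with sections 6.0, 7.5.1 and 15.6.

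*The loss is trivial beside the uncertainty in the SMD.* Largely true. The plan itself calls its use of a contrast between mild OA and healthy controls a simplification, and a move from 0.73 to about 0.75 is small against that. This limits the importance of the point, but the stated figure is still wrong.

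*The planned analysis is not the one that was powered.* Section 15.5.2.1 specifies a linear mixed-effects model on baseline, 6-month and 12-month scans, and section 15.7 relies on such models for missing data. A patient with one missed scan still contributes, so treating all 20% as wholly lost is pessimistic. This stands: 77% to 78% is the power of the comparison in section 15.6, not of the mixed model.

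*A reader might infer that the base of 30 is itself an arithmetic error.* The documents do not support that. The normal formula returns 30, and the exact t-test misses 80% by 0.6 points, or one patient. Section 15.6 names the software but not the routine used. The SMD is also rounded: at 0.7349, exact-t power with 30 per group is 79.9%. It is fair to note that a t-test calculation returns 31, and no more than that.

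**Conclusion.** The dropout inflation is wrong as written under either power method: 36 per group leaves 28.8 after the plan's own 20% loss, not 30. Power is then about 77% to 78% by exact t, or 79% by the normal approximation, against a stated 80%. The shortfall in enrolment is 2 patients per group from a base of 30, or 3 from a base of 31.

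This rests on enrolment stopping at 36 per arm, a full 20% loss with no partial information from those lost, and the unadjusted comparison named in section 15.6. If 100 are enrolled, split 50 and 50, the shortfall disappears, although the written derivation remains incorrect. A reader might therefore infer that the trial as a whole is underpowered. The documents do not support that: they leave 72 or 100 open, and the two give about 77% and about 90%.

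Severity is minor. The calculation concerns T1rho, a secondary endpoint; the primary endpoint is adverse events (sections 8.2.1 and 15.5.1), and no primary inference depends on it.

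**What to change.** - In section 15.6, replace the added 6 per group with division by 0.80: 30/0.80, rounded up to 38 per group (76 in total). If the exact t-test is the intended method, use 31/0.80, rounded up to 39 per group (78). Name the method. Enrolling 80 would fill ten of the blocks of 8 in section 15.3.
- Make the Synopsis and sections 6.0, 7.5.1 and 15.6 carry one enrolment target, with any ceiling labelled as such, and state the power that belongs to that target.
- If 36 per group is kept, restate the power as about 77% after 20% loss. If 100 is the target, state about 90%.

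The cost is wording, plus 4 to 8 additional subjects (76, 78 or 80 against 72) if the 80% is to be kept, all within the existing ceiling. If 36 is kept, the stated power becomes slightly less favourable. No analysis or safety procedure changes.
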